## 4 STATISTICAL/ANALYTICAL ISSUES

### 4.1 Adjustments for covariates

Not applicable.

### 4.2 Handling of dropouts or missing data

In general, there will be no imputation of missing data unless otherwise stated below.

Missing data will be handled as described in the sections below for safety laboratory and PK results. No other imputations will be performed.

#### 4.2.1 Pharmacokinetics

The 95% CI lower and 95% CI upper should be left blank if the standard deviation (or equivalently, the geometric CV) is 0. Measurements of PK concentrations that are below the limit of quantification (BLQ) and which are occurring prior to  $t_{max}$  will be imputed with half of the lower limit of quantification (LLOQ/2), except for embedded BLQ values (between two measurable data points) which will be treated as missing, for the purpose of calculating the geometric mean and its 95% CI, the geometric CV, the arithmetic mean and standard deviation for summaries and figures. Post- $t_{max}$ , BLQ values will be treated as missing. Descriptive statistics of concentrations will be calculated if at least 2/3rd of the individual data points are quantifiable ( $\geq$ LLOQ).

For all individual PK concentration figures, any concentrations that are BLQ will be regarded as missing, with the exception of predose BLQ measurements which will be imputed with zero (to capture lag-time) for linear scale plots.

The following rules will apply for PK data listings:

- Values below the LLOQ will be reported as “(BLQ)” in the listings

The following rules will apply for PK summaries

- Descriptive statistics of plasma concentrations will be calculated if more than 2/3rd of individual data points are quantifiable ( $\geq$ LLOQ) at the given time-point. However, if  $n < 3$ , then only  $n$ , minimum and maximum will be presented, and the median will also be presented if  $n = 3$ . The other descriptive statistics will be left blank.
- For  $t_{max}$ , only  $N$ , median, minimum and maximum will be displayed into the summary statistics,
- For plasma concentration summaries, all BLQ values will be replaced by “LLOQ/2” and missing values will be excluded.

- When the mean value includes one or more replaced BLQ values then a footnote will be included to say “contains one or more BLQ value replaced by half the LLOQ value”.
- For the individual figures, any concentrations that are BLQ will be regarded as missing, with the exception of predose BLQ measurements which will be imputed with zero for linear scale plots.
- If no study participants have data, only n=0 will be presented. The other descriptive statistics will be left blank.
- The geometric CV will be calculated using the following formula where  $SD_{\log}$  is the standard deviation from the log-transformed data:

$$\text{Geometric CV (\%)} = \text{sqrt}[(\exp(SD_{\log}^2) - 1)] \times 100$$

The PK analysis will be performed in accordance to the Guideline on performing NCA analysis dated 08 Nov 2017, and BLQ values will be treated as stated in this document for the NCA analysis.

#### **4.2.2 Safety laboratory data**

The rules for handling values that are BLQ or above the limit of quantification (ALQ) in the safety laboratory data will be the same as those described for PK data in [Section 4.2.1](#).

#### **4.2.3 Electrocardiogram data**

For the 12-lead ECG data, all calculations of changes from Baseline and descriptive statistics will be based on the mean of the triplicate assessments at each time point. In the event that there are not three available measurements at a given time point, the mean will be calculated based on the number of measurements for which data are provided.

#### **4.2.4 Dates and times**

Partial dates may be imputed for the following reasons:

- Classification of AEs as treatment-emergent
- Classification of medications as prior or concomitant

Imputed dates will not be shown in the listings; all dates will be displayed as reported in the database.

The following rules will be applied for partial start dates:

- If only the month and year are specified and the month and year of the first dose of study medication is not the same as the month and year of the start date then use the 1st of the month, or the date of screening if this is later (if the latter imputation results in an end date that is earlier than the start date, then use the 1st of the month). If time is missing this will be imputed as 00:00h
- If only the month and year are specified and the month and year of the first dose of study medication is the same as the month and year of the start date, then the date of the first dose of study medication will be used. If this results in an imputed start date that is after the specified end date, then use the 1st of the month, or the date of screening if this is later (if the

latter imputation results in an end date that is earlier than the start date, then use the 1st of the month). If the imputed date is the date of dosing then time will be imputed as the start time of the dosing (i.e., event will be regarded as treatment-emergent)

- If only the year is specified, and the year of the first dose of study medication is not the same as the year of the start date then January 01 will be used. If time is missing this will be imputed as 00:00h
- If only the year is specified, and the year of the first dose of study medication is the same as the year of the start date, then the date of the first dose of study medication will be used. If this results in an imputed start date that is after the specified end date, then January 01, or the date of screening if this is later will be used (if the latter imputation results in an end date that is earlier than the start date, then January 01 will be used). If the imputed date is the date of first dose of study medication then time will be imputed as the start time of the study medication intake (i.e., event will be regarded as treatment-emergent)

The following rules will be applied to partial stop dates:

- If only the month and year are specified, then use the last day of the month
- If only the year is specified, then use December 31 of the known year
- If the stop date is completely unknown, do not impute the stop date

Missing or partially missing dates and/or times will be imputed as described in Table 4-1 . Calculation rules for duration of adverse events can be found in Table 4-1 and will be applied for the calculation of duration of each AE. Adverse event duration is computed in and reported in day and time format: xx d hh:mm.

**Table 4-1: Calculation rules for duration of adverse events**

Data availability	Onset date/time	Outcome date/time	Calculation rules
Complete data	D1/T1	D2/T2	Duration = [(D2 – D1)*24 + (T2 – T1)]/24 d
End time missing	D1/T1	D2/--	End time is substituted by time 23:59h (=23.98 in decimal format) Duration = <[(D2 – D1)*24 + (23.98 – T1)]/24 d
Start time missing	D1/--	D2/T2	Onset time is substituted by time 00:00h Duration = <[(D2 – D1)*24 + T2]/24 d
Start and end time missing	D1/--	D2/--	Duration = <D2 – D1 + 1
Start day and time missing	--/--	D2/T2	Duration = [(D2 – D0)*24 + (T2 – T0)]/24 d For a study participant in the SS, D0 and T0 are the date and time of first administration of study medication and for screen failures, D0 is the date of the screening visit and T0 = 00:00h

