All AEs will be recorded in the CRF from the time of informed consent until study completion or termination. All AEs will be coded (see [Section 3.8](#)) and categorized by intensity (mild/moderate/severe) and relationship (related/not related) to study medication (PSL, PSL+OC, and OC) as judged by the Investigator.

All AE data will be listed by study part, treatment sequence, study participant number, start date, and time. The listings will include the following data pertaining to the AEs: start and end dates with relative days to study medication administration, duration, intensity, seriousness, relationship to study medication, action taken, and final outcome.

The number and percentage of study participants who experience TEAEs will be summarized by MedDRA SOC, PT, treatment sequence and treatment period.

Summaries of TEAEs will include the following:

- Overview of incidence of TEAEs (overview including number and percentage of study participants with any TEAEs, any serious AEs, TEAE of Special Interest, TEAEs leading to discontinuation, drug-related TEAEs, severe TEAEs and TEAEs leading to death; event counts will also be included)
- Incidence of TEAEs by maximum relationship
- Incidence of TEAEs by maximum intensity
- Incidence of non-serious TEAEs above reporting threshold of 5% of study participants

Summary tables will contain counts of study participants, percentages of study participants in parentheses and the number of events where applicable. A study participant who has multiple events in the same SOC and PT will be counted only once in the study participant counts but all events will be included.

In summaries including relationship, the following relationships will be summarized: 'Not related', 'Related'. Study participants who experience the same event multiple times will be included in the most related category for tabulations by maximum relationship. Events with missing relationship will be considered as 'Related' but recorded as missing in the listings.

In summaries including intensity, the following intensity categories will be summarized: 'Mild', 'Moderate', 'Severe'. Study participants who experience the same event multiple times will be included in the most severe category for tabulations by maximum intensity. Events with missing intensity will be considered as 'Severe' events for summary purposes but recorded as missing in the listings.

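### SAP Table 4-1 times an AE with no start day from first study dose: read literally, the duration can overrun the recorded onset month; on any reading it can be negative, and it is printed as exact

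*SAP*

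**What the plan says.** SAP Section 4.2.4 treats incomplete start dates in two places.

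**Classification rules.** These are introduced by "Partial dates may be imputed for the following reasons", and two reasons follow: deciding whether an AE is treatment-emergent, and whether a medication is prior or concomitant. Duration is not named. When only month and year are known and "the month and year of the first dose of study medication is not the same as the month and year of the start date", the onset becomes the 1st of the recorded month, or the screening date if later. In the first-dose month, the onset becomes the first dose. There is a fallback, beginning "If this results in an imputed start date that is after the specified end date", that moves the onset earlier.

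**Duration rules.** The section then says "Missing or partially missing dates and/or times will be imputed as described in Table 4-1", and that the table's rules "will be applied for the calculation of duration of each AE". The row "Start day and time missing" shows the onset as --/-- and computes [(D2 – D0)*24 + (T2 – T0)]/24 days, where "For a study participant in the SS, D0 and T0 are the date and time of first administration of study medication". It has no branch for a known month or year and no check that the end follows the first dose. The three rows that substitute only a clock time print `<` before the result; this row does not.

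**Where duration appears.** Section 10.2 puts it in the AE listings: "start and end dates with relative days to study medication administration, duration, intensity, seriousness".

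**The concern.** The same partial start date can have one onset for classification and another for duration. If the recorded month is later than the first-dose month, the duration clock starts before the earliest onset the record permits. If the AE ended before first dose, the formula subtracts a later time from an earlier one. The result is the table's crudest imputation, since a whole date is substituted rather than a clock time, yet it is the one printed without the upper-bound sign.

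At stake is the credibility of a listed item. One line could show a February onset, a 12 February end and a duration of 37 days. In Part 1 Sequence B the first study medication is the contraceptive tablet on Day 1 and PSL starts on Day 18. An AE in the PSL period would therefore carry at least 17 days (18 − 1) from before any PSL. Two programmers could also implement the row differently.

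**Working it through.** The plan gives no figure to reproduce. The check applies both sets of rules to the same illustrative AEs. Calendar dates, screening dates and an 08:00 first dose are assumptions; the rules are those of SAP Section 4.2.4 and Table 4-1.

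**1. Onset month later than first-dose month, literal reading.** Part 1 Sequence B, first dose 6 January 08:00. Day 18 is then 23 January and Day 36 is 10 February. The AE is recorded as starting in February and ending 12 February 10:00.
- Table 4-1: 12 Feb 10:00 − 6 Jan 08:00 = 37 d 02 h.
- Section 4.2.4 onset, also the earliest the record permits: 12 Feb 10:00 − 1 Feb 00:00 = 11 d 10 h.
- Excess: 25 d 16 h.

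A second case: first dose 20 November 08:00, onset December, end 10 December 12:00. Table 4-1 gives 20.17 d against 9.50 d, an excess of 10.67 d.

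**2. Range of the excess.** It equals the time from first dose to the 1st of the onset month. Every calendar start date over a year was scanned, with onset up to the last scheduled Part 1 day:

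| Sequence | Last day | Smallest | Largest |
|---|---|---|---|
| A | 44 | 0.67 d | 42.67 d |
| B | 46 | 0.67 d | 44.67 d |

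The smallest is 16 h (08:00 to midnight). The largest for B is 45 d − 8 h, and for A 43 d − 8 h.

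**3. AE ended before first dose.**
- First dose 6 Jan 08:00, end 3 Jan 12:00: −2.83 d.
- First dose 5 Dec 08:00, screening 8 Nov, onset November, end 28 Nov 12:00: −6.83 d. From the Section 4.2.4 onset (8 Nov 00:00) it is 20.50 d.
- First dose 20 Nov 08:00, screening 8 Nov, onset November, end 15 Nov 12:00: −4.83 d. From the Section 4.2.4 fallback (8 Nov 00:00) it is 7.50 d.

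If the row applies only to wholly missing starts, the last two cases are handled by Section 4.2.4. A wholly undated AE that ended before dosing still gives a negative value.

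**4. Where there is no conflict.** Onset in the first-dose month, end after first dose: first dose 20 Nov 08:00, end 25 Nov 12:00 gives 5.17 d under both rules.

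**5. Can the literal case arise?** In Part 1 Sequence B, an onset after PSL ends (Day 37 or later) is at least 36 days after first dose, so it always falls in a later calendar month. Discharge is on Day 37 or 38, so such an AE may be recalled from home. Participants are also at home for most of the washout in both sequences.

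**The case against.** The best counter-argument is that the row means a wholly missing start date. The onset is shown as --/--, and the matching row for a missing end day and time is answered in terms of a missing stop date. On that view Section 4.2.4 first completes month-only and year-only starts, Table 4-1 takes what remains, and the excess and the two-onset conflict disappear. This is a coherent reading, so the excess should be claimed only for the literal text. But the text does not say it: Section 4.2.4 confines its own imputation to classification and then names partially missing dates as going to Table 4-1. The unguarded negative value and the missing `<` survive either way.

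The affected cases are also few, and this stands. Protocol Section 8.4.1 sends occurrences between consent and first dose to medical history, so a pre-dose AE should seldom be in the AE data, although SAP Section 10.2 keeps a pre-treatment category. PSL dosing is in-clinic in both sequences. In the January example, 1 to 12 February is Days 27 to 38, mostly in confinement, where a missing start day would be unusual.

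A reader might infer that the listing would show an imputed onset under PSL, with nothing to reveal that the start is incomplete. The documents do not support that. Section 4.2.4 keeps imputed dates out of the listings and displays dates as reported, so the missing start day is visible. What is not marked is that the duration beside it is imputed.

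**Conclusion.** The rule is wrong as written, with a small effect. Read literally, it overstates duration by the time from first dose to the 1st of the onset month: 25 d 16 h in the assumed example, and 0.67 to 44.67 d over all Part 1 calendars. That part depends on partial dates going to Table 4-1, as Section 4.2.4 states. On any reading the row permits a negative duration and prints an imputed value as exact.

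The number of AEs affected cannot be derived from the documents and is probably small. Only derived durations in AE listings change. No planned TEAE summary uses duration, and TEAE classification, incidence and the PK analyses are unaffected. SAP Section 1 also limits reporting to Part 1 and a subset of outputs.

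A reader might infer that the description of severe psychiatric events as transient in Protocol Section 2.3 rests on this rule. It does not: that statement describes experience already gathered in Phase 1 and Phase 2 studies, and nothing ties it to Table 4-1.

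**What to change.** Amend the row and the sentence that leads to it:

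1. Apply D0/T0 only when the start date is wholly missing.
2. For month-only or year-only starts, calculate duration from the onset imputed under Section 4.2.4, including its end-date fallback. Using the 1st of the month for every partial date would create a new conflict, because Section 4.2.4 uses the first dose when onset falls in the first-dose month.
3. Print `<` on these imputed durations. Where first dose is the anchor, the bound presumes onset at or after first dose, in line with Section 10.2's default that AEs with missing dates are treatment-emergent.
4. Leave the duration blank if D2/T2 precedes D0/T0, as the table already does when the stop date is missing.
5. Reword the Section 4.2.4 sentence on partially missing dates to match.

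The cost is one table row, one sentence and a minor programming change. A few listed durations become shorter, become upper bounds or become blank.

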**Table 4-1: Calculation rules for duration of adverse events**

Data availability	Onset date/time	Outcome date/time	Calculation rules
End day and time missing	D1/T1	--/--	If the stop date is missing, duration will not be calculated.
Start and end date missing	--/--	--/--	If the stop date is missing, duration will not be calculated.

### 4.3 Handling of repeated and unscheduled measurements

All repeated and unscheduled measurements will be presented in the data listings, where applicable. The following general rules will apply to all repeated and unscheduled measurements:

- For repeated measurements obtained prior to the first dose of study medication the latest value (which may be scheduled or unscheduled) will be used in the calculation of the descriptive statistics
- For repeated measurements obtained at the designated Baseline visit, the latest value (which may be scheduled or unscheduled) will be defined as the Baseline provided that this occurred prior to the first dose of study medication
- Unscheduled and repeated measurements will not be used in the descriptive statistics at time points after first dose of study medication
- Unscheduled measurements performed for the End of Study/Safety-Follow-Up/Early Discontinuation Visit (EOS/SFU/EDV) visit will be assigned to the EOS/SFU/EDV Visit (Section 4.4) and analyzed accordingly as an EOS/SFU/EDV Visit.

### 4.4 Handling of measurements obtained at the early withdrawal visit

Study participants who withdraw early from the study for any reason, including those withdrawn from study medication, will be asked to return for the EOS/SFU/EDV Visit as soon as possible after the last dose of study medication.

### 4.5 Interim analyses and data monitoring

Not applicable.

### 4.6 Multicenter studies

This study is planned to be conducted at one site. Thus, there is no plan to explore sites effect in the analysis.

### 4.7 Multiple comparisons/multiplicity

Not applicable.

### 4.8 Use of an efficacy subset of study participants

Not applicable.

---

## **4.9 Active-control studies intended to show equivalence**

Not applicable.

## **4.10 Examination of subgroups**

Not applicable

# **5 STUDY POPULATION CHARACTERISTICS**

## **5.1 Study participant disposition**

The number of study participants who signed the informed consent and study participants who were screen failures, completed or prematurely discontinued the study, as well as the reason for discontinuation will be summarized separately per study part for all study participants, based on the ASP. A study participant who completed the study is defined as a study participant who completed all visits up to and including the EOS/SFU/EDV visit. If there is more than one termination due to AE, then an additional table summarizing the discontinuations due to AE will be produced. In case that only one subject discontinues due to AE, then this will be presented in a listing. The number of study participants screened, number of screen failures and primary reason for screen failure will be summarized based on the ASP.

The number and percentage of study participants included in each of the analysis sets will be summarized based on All Study Participants. Percentages will be calculated based on All Study Participants for the purpose of this summary.

In addition, the following listings will be presented:

- Study participant disposition (All Study Participants) - including screening failure reasons
- Study participant analysis sets (All Study Participants)

The listing of study participant disposition will include the date of informed consent, the date of randomization, date and time of first and last dose of PSL, date and time of first and second dose of OC, date of premature termination and primary reason (if applicable).

## **5.2 Protocol deviations**

Important protocol deviations will be identified and classified by the deviation types in the IPD document (see also section 3.4). A listing of all IPDs identified at the DEM will be presented by study part and treatment sequence for all study participants based on the SS and will include the deviation type and description.

# **6 DEMOGRAPHICS AND OTHER BASELINE CHARACTERISTICS**

## **6.1 Demographics**

A by-study participant listing of demographics will be presented by study part, treatment sequence (Sequence A, Sequence B) based on All Study Participants. This will include the year of birth, age (in years), sex, race, ethnicity, country, height (in cm), weight (in kg) body mass

index (BMI, in kg/m^2). The body weight will be the measurement obtained at Screening. Body mass index (kg/m^2) is documented in the CRF.

All demographic characteristics (except for year of birth) will be summarized separately for each study part by treatment sequence and overall (Sequence A, Sequence B and All Study Participants) based on the SS. The summary of age will include descriptive statistics and categorical summaries, the latter based on requirements for European Union Drug Regulating Authorities Clinical Trials (EudraCT) and clinicaltrials.gov reporting.

For the EudraCT reporting, the categories will include:

- 18 to <65 years
- 65 to <85 years
- ≥85 years

For clinicaltrials.gov reporting, the categories will include:

- ≤18 years
- 19 to <65 years
- ≥65 years

Characteristics about childbearing potential and method of birth control will be listed by study part and treatment sequence for study participants in the ASP.

## 6.2 Other Baseline characteristics

Lifestyle characteristics including data regarding alcohol, caffeine, and tobacco use will be listed.

## 6.3 Medical history, procedure history and concomitant medical procedures

Medical history will be listed (by study part) and summarized (in separate incidence tables per study part) for the SS, by MedDRA system organ class (SOC) and preferred term (PT) per treatment sequence and overall. The reported term will be included in the listing. The summary will include the number and percentage of study participants, and will be sorted alphabetically by SOC and by descending incidence of PT within each SOC, based on the 'All Participants' column.

